BIOMEDICAL RESEARCH PROTOCOL (VMU)

1. Title of Biomedical Research

„Ambient air and noise pollution effect on cardiovascular health risk and lifestyle intervention to attenuate it in 45–64-year population“ (METSGREEN) is a part of the international study “*Noise and/or ultrafine particulate matter induced cerebral and cardiovascular damage: novel insights from experimental and epidemiological studies and computational models*”

Protocol Number: 1

Version: 3

Date: 2025-03-19

2. Hypothesis of the METSGREEN Biomedical Research

Ambient ultrafine particles in the living environment increases the risk of cardiovascular diseases (CVD) among residents aged 45–64, however, this risk can be reduced by increasing physical activity in green spaces.

3. Aim of the Biomedical Research

Primary Objective (Observational Study):

To determine the association between ambient exposure to ultrafine (PM0.1) particulate, as well as noise, and the risk of cardiovascular diseases (CVD) among 45–64-year-old residents of Kaunas.

Secondary Objectives (Experimental Clinical Trial):

- ✓ To determine the association between ultrafine particulate concentrations and key indicators of metabolic syndrome.
- ✓ To assess the impact of physical activity in green spaces and healthy nutrition on individuals with central obesity and elevated blood pressure.
- ✓ To provide recommendations for reducing the risk of metabolic disorders.

4. Objectives

Objectives of the Observational Study involving 1,000 participants:

To measure and model the levels of air pollution and noise exposure in Kaunas, and to determine the relationship between individual exposure and CVD risk, depending on the participants' social and economic status.

To assess the long-term impact of road traffic intensity, PM0.1 and noise exposure on key indicators of metabolic disorders.

Objectives of the Experimental Clinical Trial (180 Participants)

To determine the impact of a healthy lifestyle (physical activity in green spaces and the Mediterranean diet) on indicators of metabolic disorder risk and to provide recommendations for reducing the risk of metabolic disorders.

5. Detailed Description of the Biomedical Research Outcomes (Primary and Secondary Endpoints)

Primary Endpoints:

Measured concentrations of PM0.1 and noise levels in 20 locations across the city of Kaunas. Using a land-use regression (LUR) model, exposure levels for 1,000 participants will be modelled and linked to self-reported health outcomes: prevalence of CVD, blood pressure, waist circumference, and anthropometric data.

Secondary Endpoints:

During the experimental clinical trial (7-day healthy lifestyle intervention), involving 180 participants, key indicators of metabolic disorders will be assessed, including waist circumference and blood pressure measurements, high-density lipoprotein (HDL) levels, triglycerides, plasma glucose concentration, as well as biological markers from metabolomics, proteomics, and DNA methylation. These will be analyzed in relation to environmental exposure, socioeconomic status, and healthy lifestyle factors. Recommendations will be developed for reducing the risk of metabolic disorders.

6. Justification for the Biomedical Research

The international research's "Noise and/or ultrafine particulate matter induced cerebral and cardiovascular damage: novel insights from experimental and epidemiological studies and computational models" (MARKOPOLY) part conducted at Vytautas Magnus University (VMU), title: "Ambient air and noise pollution effect on cardiovascular health risk and lifestyle intervention to attenuate it in 45–64-year population" (METSGREEN), is being conducted to the order of the European Commission, which provides the necessary funding for its implementation. The MARKOPOLY is coordinated by Johannes Gutenberg University in Germany.

Environmental exposures increase health risk factors and account for up to two-thirds of all chronic non-communicable diseases¹. Environmental-related risk factors, among them air pollution, and personal lifestyle habits can contribute to the increase the global burden of CVD such metabolic syndrome, arterial hypertension, and diabetes mellitus. In Europe, approximately 500,000 premature deaths occur annually due to air pollution. However, particulate matter and noise thresholds are not currently incorporated into clinical guidelines. Moreover, the official European environmental pollution limits significantly exceed the standards set by the World Health Organization (WHO). This issue is especially critical for the most vulnerable populations—those affected by social exclusion, chronic illnesses, or advanced age.

METSGREEN study will use clinical and mathematical models, environmental epidemiology methods, and exposure-response modelling to generate new scientific data on the relationship between PM0.1 exposure and changes in biological markers of metabolic disorders, particularly

in the context of healthy lifestyle interventions. The findings will support the development of preventive programs and measures aimed at reducing the risk of metabolic disorders.

The role of PM0.1 exposure in the pathogenesis of metabolic disorders that promote the development of CVD and metabolic syndrome remains unclear. When comparing the health effects of fine and coarse particulate matter, the damage caused by PM0.1 is greater due to its ability to directly penetrate lung tissue and enter the bloodstream. This leads to systemic inflammation, endothelial dysfunction, coagulation abnormalities, and oxidative stress—processes that contribute to the development of metabolic disorders and CVD.¹ In Lithuania, cardiovascular diseases affect approximately 40% of the population aged 45–64 and have a significant impact on public health and the healthcare system². Central obesity is the most important indicator of metabolic disorder; however, data on its association with PM0.1 exposure levels and individual health behaviours are lacking. According to the joint recommendation of international scientific societies on the diagnosis of metabolic syndrome, the key diagnostic criteria include central obesity, elevated blood pressure, increased plasma glucose concentration, elevated triglyceride levels, and low high-density lipoprotein (HDL) cholesterol concentration.³ Early identification and management of metabolic syndrome can significantly reduce the risk of CVD and fatal outcomes⁴. Physical activity in green spaces can improve health by reducing stress responses and through the regulation of brain-derived neurotrophic factor (BDNF), enhancing cardiac function and lowering blood pressure. Regular 30-minute walks combined with a healthy dietary intervention can significantly improve heart function, reduce blood pressure, and lower body mass index (BMI)^{5,6}. There is a link between central obesity, body mass index, and biological markers associated with cardiometabolic disorders, as well as blood pressure and the prevalence of hypertension⁷. There are some evidences that physical activity in green space (Nature therapy) produces an opportunity to decrease the risk for obesity, other chronic diseases and can mitigate the negative effects of environmental exposure⁸. However, evidence and frameworks to implement nature-based therapies for metabolic syndrome are scarce. Thus, the investigation of metabolic disorder pathophysiology and the reduction of these disorders through physical activity in green spaces represent one of the modern and promising approaches of nature therapy. Based on the METSGREEN study results, we will provide recommendations for reducing the risk of metabolic disorders, both for public health professionals involved in population health monitoring and for the public.

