Observational Study Participants: The study will include men and women aged 45–64 who are residents of Kaunas City and live in private apartments. Approximately 1,000 individuals will be randomly selected. Individuals living in institutions, rented accommodations, or nursing homes will be excluded from the study.

Experimental Clinical Trial Participants – Inclusion Criteria: Participants must be aged 45–64, male or female, residents of Kaunas City, and randomly selected from the observational study cohort. They must agree to wear a smart wristband sensor for 7 days and sign an informed consent form to participate in the healthy lifestyle intervention. A total of 180 participants will be enrolled.

Exclusion Criteria for Clinical Trial: Participants will be excluded if they have unstable angina, cardiomyopathy, hypertension with blood pressure greater than 160/110 mmHg, cardiac pacemakers, neurological diseases, alcohol dependence, limited mobility, or if they are pregnant.

Justification for Sample Size: The experimental clinical trial involving 180 participants will be conducted by researchers at VMU. The trial will assess the impact of a healthy lifestyle on early metabolic responses (biomarkers and health risks), considering individual PM0.1 exposure levels. To enhance data reliability and reducing the risk of Type I error (false positive) the confidence level is set up at 99.9%. The sample size was calculated using the formula:

$$N=2\times(Z_{1-\alpha/2}+Z_{1-\beta}/\delta_0)^2 \times p \times (1-p),$$

Where:

- N = required sample size
- $Z_{1-\alpha/2} = 3.29$ (for a 0.1% significance level)
- $Z_{1-\beta} = 0.842$ (for 80% statistical power)
- $\delta_0 = \text{effect size} = 0.1$
- $p = \text{expected proportion} = 0.3$

This gives:

$$N \approx 2 \times (3.29 + 0.842 / 0.1)^2 \times 0.3 \times 0.7 \approx 58 \text{ participants}$$

To account for potential dropouts (e.g., due to acute infections), a sample size of 60 per group is proposed. Therefore, a total of 180 participants will be enrolled in the clinical trial.

8. Biomedical Research Methodology

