Measures to Reduce Subjective Bias: Participants will be randomly assigned to the three clinical trial groups. Only individuals without the listed health exclusions and who sign informed consent will be included. Assignment to the one of three groups will follow a 1:1:1 ratio. The researcher will handle group allocation and coding. Objective environmental pollution measurements and individual residential exposure will be taken. Seven-day monitoring health outcomes include physical activity, sleep disturbances, heart function. Two health checks will include measurements of blood pressure, body composition, waist circumference, body mass index (BMI) and biomarkers. Blood samples (up to 20 ml) will be collected to analyse metabolic biomarkers.

Mathematical modelling will be used during data analysis. It will control for confounding factors to assess the strength of the exposure–health outcome relationship.

Biomedical Study Plan: The study plan and phases are shown in Figure 1.

Observational Study: A representative sample survey of Kaunas residents will be conducted by a certified survey company that complies with strict personal data security, privacy principles, and legal requirements. In accordance with the General Data Protection Regulation (GDPR), data will be securely stored, lawfully processed, and participants will be able to exercise their rights easily. The internet survey will be conducted using the Google Forms platform, which provides data encryption and access control (limited to authorized personnel). Google services comply with EU data protection regulations, including two-factor authentication, ensuring the confidentiality and security of personal data. Approximately 1,000 individuals aged 45–64 will be included based on their responses to an anonymous online survey, which collects self-reported health indicators (physician-diagnosed chronic diseases), socioeconomic status, and basic residential information.

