Experimental Clinical Trial: Participants who completed the online survey and conform to the study inclusion criteria will be eligible. Those interested in participating in the healthy lifestyle clinical trial can contact the researchers via the details provided in the internet survey form. Upon contact, participants will be asked to updated information on waist circumference, blood pressure, and address. Eligible participants will be invited to the Family Medicine Clinic of Kaunas Clinics at the Lithuanian University of Health Sciences (LSMU).

Inclusion criteria: Age 45–64, residence in Kaunas City on streets with identified high air pollution levels, and self-reported metabolic disorder indicators such as increased waist circumference and/or elevated blood pressure. Following contact, appointment times will be coordinated. At the initial visit, researchers will review the participant's health status. Participants will be informed about the experimental clinical trial and will sign an informed consent form. They will then be randomly assigned to one of three healthy lifestyle groups and instructed on their 7-day health behaviour study. Groups: 1. Control group (usual routine); 2. Physical activity in green space (daily 30-minute brisk walk); 3. Mediterranean diet intervention.

All groups' participants health assessments will be conducted by family doctor on Day 1 and Day 8 using certified medical equipment. Participants will be asked to arrive fasting or having not eaten for at least 2 hours before their visit.

Procedures will include:

- Blood sampling (up to 20 ml) for analysis of metabolic biomarkers
- Blood pressure measurement
- Waist circumference measurement
- Body composition analysis

All participants will wear Fitbit Alta wristband sensors for 7 days, which will collect digital data on physical activity (METs), step count, heart rate, sleep quality. Collected data will be transferred to a secure digital platform and coded to assess the results.

[figure not shown]

Fig. 1 Scheme of the Kaunas Clinical study

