Each group's clinical health indices and metabolic responses will be assessed by measurements blood pressure, waist circumference, high-density lipoproteins (HDL), triglycerides, plasma glucose levels, also metabolomic, proteomic, and DNA methylation biomarkers before and after the 7-day intervention. Primary proteomics screening comprises of 4–6 oxidative stress and inflammation markers via immunoblotting. In a second phase, based on the initial results, advanced OMICs analysis will be conducted using high-resolution techniques, such as redox/phospho-proteomics, metabolomics, DNA methylation via EPIC chip (for genome-wide methylation analysis). All data will be analysed using mathematical modelling to account for confounding variables. Results will substantiate recommendations for reducing metabolic disorder risks, targeted to healthcare professionals and the public.

Data Analysis and Evaluation: Both the observational and experimental clinical studies will use a standardized exposure–health response analysis approach. Key methods: multivariate logistic regression analysis, adjustment for confounding factors using mathematical modelling to estimate the strengths of the relationship and 95% confidence intervals between the variables.

Biological samples for metabolic response analysis will be sent to accredited partner laboratories:

- DNA methylation analysis: National Center of Pathology (Lithuania), Laboratoire National de Santé (Luxembourg)
- Proteomic analysis: University of Southern Denmark (Odense, Denmark)

- Metabolomic analysis: Institute for Molecular Sciences, University of Eastern Finland (Finland)

9. Description of Study Sites and Institutions Involved in Biomedical Research Activities

The METSGREEN biomedical research is being conducted together with 15 international scientific MARKOPOLY project centres, as part of an international collaboration. The participating institutions are:

1. Universitätsmedizin der Johannes Gutenberg-Universität Mainz (Germany) – *Coordinator*
2. Università degli Studi di Padova (Italy)
3. Medical University of South Carolina (United States)
4. Vytautas Magnus University (Lithuania)
5. University of Belgrade, Faculty of Medicine (Serbia)
6. The Cyprus Institute (Cyprus)
7. Concentris research management gmbh (Germany)
8. Max Planck Society for the Advancement of Science (Germany)
9. Laboratoire National de Santé (Luxembourg)
10. Luxembourg Institute of Health (LIH) (Luxembourg)

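### The randomised trial names no primary endpoint or contrast, and its sample size rests on an unnamed proportion at an error level that the analysis section does not use

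*Protocol*

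**What the plan says.** Section 3 places the trial under the label "Secondary Objectives (Experimental Clinical Trial"; the primary objective is observational. Section 5 follows the same split. Its primary endpoints are the pollution and noise measurements, from which "exposure levels for 1,000 participants will be modelled and linked to self-reported health outcomes: prevalence of CVD, blood pressure, waist circumference, and anthropometric data". For the trial, Section 5 says that "key indicators of metabolic disorders will be assessed, including waist circumference and blood pressure measurements" and continues with "high-density lipoprotein (HDL) levels, triglycerides, plasma glucose concentration, as well as biological markers from metabolomics, proteomics, and DNA methylation". Nothing in that list is ranked, and Section 8 repeats it without ranking.

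Section 8 defines the arms: "Groups: 1. Control group (usual routine); 2. Physical activity in green space (daily 30-minute brisk walk); 3. Mediterranean diet intervention". It adds that "Assignment to the one of three groups will follow a 1:1:1 ratio". No comparison between arms is named as the main one. The hypothesis in Section 2 mentions only activity in green space, whereas the trial objective in Section 4 covers both activity and diet.

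The sample-size text in Section 7 states: "To enhance data reliability and reducing the risk of Type I error (false positive) the confidence level is set up at 99.9" per cent. It then uses Z values of 3.29 and 0.842, an effect size of 0.1 and an expected proportion of 0.3, and arrives at 58, rounded up to 60 per group. The data analysis paragraph in Section 8 covers the survey and the trial together. It plans logistic regression "to estimate the strengths of the relationship and 95% confidence intervals between the variables".

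**The concern.** A trial with its own randomisation, control arm and power calculation needs one question that the size was chosen to answer. Here the reader cannot tell which outcome, in which comparison, 60 per group is meant to support. The calculation needs a binary outcome, and so does logistic regression, but the trial endpoints are listed as measurements and no responder or metabolic-syndrome outcome is defined.

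Two things are at stake. The stated power attaches to no identifiable result. And with many unranked outcomes across three arms, the protection against false positives depends on which error level is applied, a point on which Sections 7 and 8 disagree. The trial's results are meant to support recommendations to health professionals and the public, so the question should be fixed before the data are seen.

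**Working it through.** **1. The plan's own figure.** Inputs from Section 7: Z = 3.29 (0.1% two-sided), Z = 0.842 (80% power), effect 0.1, proportion 0.3.

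As printed: 2 × (3.29 + 0.842/0.1)² × 0.3 × 0.7 = 2 × 11.71² × 0.21 = 57.6, which rounds to the stated 58.

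This result arises only because 0.1 divides the power term alone. With the whole sum divided by 0.1: 2 × (4.132/0.1)² × 0.21 = 2 × 41.32² × 0.21 = 717 per group. Power at 60 per group for a difference of 0.1 from 0.3 is about 2% at the 0.1% level, and 21% (0.3 v 0.4) to 24% (0.3 v 0.2) at the 5% level. So 60 per group does not give 80% power for that difference at either level, whatever the proportion stands for.

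**2. Chance of at least one false positive.** Section 5 lists five clinical indicators: waist, blood pressure, HDL, triglycerides and glucose. Two contrasts with control give 5 × 2 = 10 tests. The calculation assumes that each is tested without adjustment and that no arm has any effect.

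If the ten tests were independent:
- 5% level: 1 − 0.95¹⁰ = 40.1%
- 0.1% level: 1 − 0.999¹⁰ = 1.0%

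The contrasts share a control arm and the outcomes are probably correlated. The documents give no correlations, so a range is assumed. Simulation with three equal arms and 400,000 draws gives:

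| Outcome correlation (assumed) | 5% level | 0.1% level |
|---|---|---|
| 0 | 37.7% | 0.98% |
| 0.3 | 35.1% | 0.96% |
| 0.5 | 30.9% | 0.91% |
| 0.7 | 25.6% | 0.77% |

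Using all three pairwise comparisons raises the ranges to 33–48% and 1.1–1.4%. Counting systolic and diastolic pressure separately, with two contrasts, gives 28–44% and 0.9–1.2%.

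**3. What 60 per arm can detect.** For a continuous endpoint compared between two arms of n = 60, the standardised difference is (Z₁₋α/₂ + Z₁₋β) × √(2/n), with √(2/60) = 0.1826.
- 2.5% per contrast (two contrasts sharing 5%): (2.241 + 0.842) × 0.1826 = 0.56 SD
- 5%, single contrast: (1.960 + 0.842) × 0.1826 = 0.51 SD
- 0.1% per contrast: (3.291 + 0.842) × 0.1826 = 0.75 SD

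These are before baseline adjustment, which would reduce them, and before dropout, which would increase them.

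**The case against.** **The false-positive risk may be small.** A reader might infer that the trial runs a false-positive risk of a quarter or more. The documents do not establish that. If the 99.9% level governs, the risk over the five indicators is about 1%. That is still several times 0.1% as a ratio, but low in absolute terms. Section 8 mentions 95% intervals; it states no 5% test between arms and no rule for declaring success. So the inference that any one favourable contrast would count as the trial's success goes beyond the text. A multiplicity procedure may also sit in a SAP that is not shown, and its absence here is no finding. This objection stands, and it limits the error-rate part to a conditional statement.

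**The protein markers should not be counted.** Adding the 4–6 protein markers would give 18–22 tests, and 1 − 0.95¹⁸ = 60% to 1 − 0.95²² = 68% if all were independent. Section 8 describes these markers as an initial screen that guides later omics work, and independence among them is doubtful. Those figures are not relied on.

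**A proportion fits the planned analysis.** Logistic regression needs a binary outcome, and the background in Section 6 describes the metabolic-syndrome criteria in terms of elevated or low values. A reader might therefore say that the calculation uses the wrong type of outcome, but the text does not show this. The supportable statement is that the binary outcome is never named.

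**The main question can be guessed.** The hypothesis points to walking against control, and Section 6 calls central obesity the most important indicator. Neither is declared primary, and the trial objective gives diet equal standing. This does not fill the gap.

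**A SAP could supply the primary endpoint.** This carries little weight. The sample size depends on the choice, and this protocol has a section for primary and secondary endpoints that gives the trial no primary one.

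**Conclusion.** The point holds in this form: the randomised trial has no primary endpoint and no primary contrast, its sample size is tied to a proportion that is never named, and the 99.9% level in Section 7 is not reconciled with the 95% intervals in Section 8. These three statements rest on the protocol text alone.

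The error-rate figures, about 26–38% at the 5% level and about 1% at the 0.1% level, are conditional. They assume five indicators, two contrasts with control, no adjustment, and an outcome correlation between 0.7 and 0. They show why the two levels must be reconciled and do not forecast what the trial will report.

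The bracket error behind the 58 is a separate fault that naming an endpoint would not cure. It matters here because the present power statement cannot simply be attached to whichever endpoint is chosen. The sponsor should make the change before any trial outcome data are examined.

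**What to change.** 1. Name one primary trial endpoint measured in all 180 participants, for example Day 8 systolic blood pressure adjusted for Day 1. If it is continuous, analyse it by linear regression (ANCOVA) instead of logistic regression.
2. Name walking v control and diet v control as the two primary contrasts, tested with Holm or Dunnett at one stated family-wise level. Use that level in both the sample-size text and the analysis text.
3. List the other clinical indicators as secondary, and the omics as exploratory with false-discovery-rate control.
4. Withdraw the statement that 58 per group gives 80% power for a difference of 0.1 at the 0.1% level. State instead the difference detectable with 60 per arm: about 0.56 SD at 80% power with 2.5% per contrast, before baseline adjustment and dropout. Give an SD for the chosen endpoint, with its source, so that this can be read in clinical units; the protocol gives none.

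**Cost.** Protocol wording and the approvals that Section 19 requires for a modification; no extra participants. The other indicators lose confirmatory status, and the stated precision becomes less favourable than the protocol now implies. If the sponsor wants to keep a difference of 0.1 in a proportion at the 0.1% level, wording alone will not do, because the standard formula then asks for about 717 per group.

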15. Potential Benefits of the Biomedical Research to the Participants

Participants in the biomedical research will not receive direct personal benefit. However, those taking part in the experimental clinical trial may experience indirect benefits. The participant groups will be analyzed and described in detail, and everyone's body composition will be assessed—providing insights into their metabolic condition and cardiovascular disease (CVD) risk. Additionally, anonymized data collected from the study will contribute to the development of preventive strategies aimed at improving public health and reducing CVD risk at the population level.

16. Assessment of Possible Risks and Inconveniences to the Participants

Participation in the experimental biomedical study is expected to involve only minimal inconvenience. Daily routines will not be significantly disrupted, as the interventions involve 30-minute walks in a park or following a Mediterranean diet—both of which are middle in intensity and easy to integrate into daily life. The time commitment will be relatively small, not exceedingly approximately 2 hours in total. Venous blood sampling (approximately 20 ml) may cause minor discomfort. All data will be processed anonymized, using participant codes in accordance with personal data protection regulations. The electronic database linking participants' names to their assigned codes will be securely stored by the principal investigator on a password-protected computer. Only the principal investigator and an authorized researcher will have access to this information.

17. Procedure for Documentation and Evaluation of Adverse Events Observed During the Biomedical Research

The anonymous online questionnaire survey involving 1,000 individuals is not expected to cause any adverse events. In the experimental clinical trial involving 180 participants, venous blood sampling (up to 20 ml) is considered safe and non-harmful to health; therefore, no adverse events related to the procedure are anticipated. In the unexpected reaction, the physician-investigator will

provide immediate medical assistance. A report form documenting the incident will be completed, and the participant's family physician will be informed accordingly.

18. Processing of Personal Data, Assurance of Participant Confidentiality, and Personal Data Protection (this section must address all the questions listed below):

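### The protocol states an exposure-response model and a within-group before-after look for the randomised trial, but never the walking-versus-control and diet-versus-control comparisons

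*Protocol*

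**What the plan says.** Four places in the protocol bear on how the trial outcomes are analysed.

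- **Section 5, Secondary Endpoints.** After listing the trial outcomes (waist, blood pressure, HDL, triglycerides, glucose and the omics markers), it says: "These will be analyzed in relation to environmental exposure, socioeconomic status, and healthy lifestyle factors". Assigned group is not named.
- **Section 8, Data Analysis and Evaluation.** One approach serves both parts of the study: "Both the observational and experimental clinical studies will use a standardized exposure–health response analysis approach". The method follows: "Key methods: multivariate logistic regression analysis, adjustment for confounding factors using mathematical modelling", with 95% confidence intervals.
- **Section 8, after Figure 1.** "Each group's clinical health indices and metabolic responses will be assessed by measurements blood pressure, waist circumference" and the laboratory markers, "before and after the 7-day intervention". This is the only group-wise analysis described.
- **Section 15, Potential Benefits.** "The participant groups will be analyzed and described in detail". No comparison is defined.

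The design is set out separately. The trial objective in Section 4 is "To determine the impact of a healthy lifestyle (physical activity in green spaces and the Mediterranean diet) on indicators of metabolic disorder risk". Section 8 randomises participants 1:1:1 to a usual-routine control, a daily walk in green space, or a Mediterranean diet. All participants wear a wristband during the week, "which will collect digital data on physical activity (METs), step count, heart rate, sleep quality".

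**The concern.** The objective asks what the interventions do. A 1:1:1 randomisation with a usual-routine control answers that through two differences: walking minus control and diet minus control. Neither difference is stated, and neither analysis that is stated delivers it.

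An exposure-response regression with confounder adjustment is a survey analysis. It needs adjustment because people were not assigned their exposure, and its validity depends on having measured every relevant confounder. A before-after change within one group is uncontrolled. Familiarity with the clinic at a second visit, the effect of being observed and wearing a sensor, and ordinary week-to-week variation can move all three groups. Only subtracting the control group's change removes them.

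The results are to support recommendations to health professionals and the public. An analysis plan that followed Sections 5 and 8 literally could report associations and within-group changes as intervention effects.

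**Working it through.** The point turns on text, and the plan gives no figure for it. The check is whether any stated analysis yields a between-arm contrast.

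**1. Stated analyses against what the design needs**

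| Place in protocol | Explanatory variable or comparison stated | Uses the control group? |
|---|---|---|
| Section 5 | Exposure, socioeconomic status, lifestyle factors | Only if the last term means assigned group |
| Section 8, data analysis | Exposure-response, adjusted for confounders; no arm term named | Not stated |
| Section 8, group assessment | Before versus after, each group | No |
| Section 15 | Groups analysed and described | Not stated |
| Needed by Section 4 objective and Section 8 design | Walking v control; diet v control | Yes |

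The first four rows contain no explicit between-arm contrast, no arm term in a model and no statement that people are analysed as randomised.

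**2. The ambiguous term in Section 5**

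- *Assigned group.* Sections 4, 5 and 8 use the healthy-lifestyle label for the intervention and the three arms. On this reading the arm is among the explanatory variables.
- *Measured behaviour before randomisation.* Section 18 says the trial also holds self-reported questionnaire data, which include smoking and physical activity. Adjusting for these does no harm, but they are not the intervention.
- *Measured behaviour during the week.* The wristband records METs and steps after randomisation, and the assigned walk may change them.

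The first reading estimates the effect of assignment. The third estimates an association with achieved activity. The protocol does not choose between them.

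**3. Illustration of why the choice matters (assumed inputs)**

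The group size of 60 comes from Section 7. Everything else here is an assumption: no true arm effect; assigned walking raises step count by 0.8 SD; a fitness factor correlates r with step count within arm and r with the Day 8 outcome; two-sided 5% test; linear model.

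Correlation of steps with outcome in 60 + 60 people: ρ = r² / √(1 + 0.8² × 0.25) = r² / √1.16.

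- r = 0.3: ρ = 0.09 / 1.077 = 0.084. Fisher z = 0.0838 × √117 = 0.91. Chance of significance about 15%.
- r = 0.5: ρ = 0.25 / 1.077 = 0.232. Fisher z = 0.2364 × √117 = 2.56. Chance of significance about 72%.

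A simulation with 4,000 repeats per setting gave 15% and 71%. The as-randomised difference averaged 0.00 SD and was significant in about 5% of repeats.

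Conversely, if walking worked wholly through recorded activity, with a true arm effect of about 0.24 to 0.39 SD, adding step count beside the arm would take the arm estimate to about 0.00 SD. That follows from the assumption of full mediation. None of these figures is an error rate for this trial.

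**The case against.** The strongest reply is that the protocol plainly intends a comparison by arm. It has a control group, an objective framed as the impact of the intervention, a sample size set per group with a two-group formula (Section 7), an assessment of each group (Section 8) and a statement that the groups will be analysed (Section 15). Because the healthy-lifestyle label names the arms elsewhere, the phrase in Section 5 may well include assignment. Relating trial outcomes to exposure is also legitimate in itself: Section 3 lists the association of ultrafine particles with metabolic syndrome indicators under the trial's secondary objectives. Details such as handling of non-adherence are commonly left to an analysis plan, and one may exist.

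Much of this stands. A reader might infer that the protocol abandons randomisation, or that it will regress outcomes on step count. The documents support neither. No section enters steps or METs as an explanatory variable, and Section 8 lists physical activity among the monitored outcomes.

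The reply does not remove the point. Intention has to be pieced together from the design sections, while the sections that state the analysis give a different one. This is more than silence left for an analysis plan to fill: the protocol fixes a method for the trial, and an analysis plan faithful to it would inherit that method.

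**Conclusion.** The concern holds in a limited form. The only model specified for the randomised trial is the confounder-adjusted exposure-response regression it shares with the survey, and the only group-wise analysis described is before-after within each group. The two contrasts with control are never stated, and one explanatory term can mean either assigned group or measured behaviour.

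It would go too far to say that the protection of randomisation is given up, since an arm comparison is compatible with the text and implied by the design. The size of any harm depends on which reading the analyst adopts and cannot be computed from the protocol; the 15% to 72% range illustrates one unfavourable reading under assumed correlations. The change is worth making before analysis because it replaces a stated observational or uncontrolled analysis with the randomised one at no cost.

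**What to change.** In Sections 5 and 8, state that:

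- Trial outcomes at Day 8 are compared between the three groups as randomised, with walking versus control and diet versus control named as the contrasts, and each person counted in the assigned group.
- The model includes the Day 1 value of the outcome and, if wanted, other pre-randomisation covariates only.
- PM0.1 and socioeconomic status are baseline covariates or effect modifiers, serving the separate exposure objective.
- Intervention-week wristband data are used to describe adherence, as an outcome, or in a labelled explanatory analysis, and not as an adjustment in the arm comparison.
- The lifestyle-factors wording in Section 5 is replaced by assigned group, with any baseline behaviours listed separately.
- Within-group before-after changes are descriptive.

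The cost is a few sentences in the protocol, carried into the analysis plan, plus the ethics approval that Section 19 requires for protocol changes. No extra participants, visits, samples or data are needed.
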